#### **4.2 Dosing delays, support care, and discontinuation of therapy**

There will be no dose modifications allowed for management of toxicities.

Nivolumab administration should be delayed for the following until resolution to  $\leq$  Grade 1:

- Any Grade  $\geq 2$  non-skin, drug-related adverse event, with the following exceptions:
  - Grade 2 drug-related fatigue or laboratory abnormalities do not require a treatment delay
  - Any Grade 3 skin, drug-related adverse event
  - Any Grade 3 drug-related laboratory abnormality, with the following exceptions for lymphopenia, leukopenia, AST, ALT, or total bilirubin:
    - Grade 3 lymphopenia or leukopenia does not require dose delay
    - If a subject has a baseline AST, ALT or total bilirubin that is within normal limits, delay dosing for drug-related Grade  $\geq 2$  toxicity
    - If a subject has baseline AST, ALT, or total bilirubin within the Grade 1 toxicity range, delay dosing for drug-related Grade  $\geq 3$  toxicity
- Any adverse event, laboratory abnormality, or intercurrent illness which, in the judgment of the investigator, warrants delaying the dose of study medication.

Immuno-oncology (I-O) agents are associated with AEs that can differ in severity and duration than AEs caused by other therapeutic classes. Nivolumab is considered an immuno-oncology agent in this protocol. Early recognition and management of AEs associated with immuno oncology agents may mitigate severe toxicity. Management Algorithms have been developed to assist investigators in assessing and managing the following groups of AEs:

- Gastrointestinal
- Renal
- Pulmonary
- Hepatic
- Endocrinopathy
- Skin
- Neurological

The above algorithms are found in the nivolumab Investigator Brochure and appendix D of this protocol.

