##### **4.2.1 Treatment discontinuation criteria**

Nivolumab treatment should be permanently discontinued for the following:

- Any Grade 2 drug-related uveitis, eye pain or blurred vision that does not respond to topical therapy and does not improve to Grade 1 severity
- Any Grade 3 non-skin, drug-related adverse event lasting > 7 days
- Grade 3 drug-related uveitis, pneumonitis, bronchospasm, hypersensitivity reaction, or infusion reaction of any duration requires discontinuation
- Grade 3 drug-related laboratory abnormalities do not require treatment discontinuation except:
  - Grade 3 drug-related thrombocytopenia > 7 days or associated with bleeding requires discontinuation
  - Any drug-related liver function test (LFT) abnormality that meets the following criteria requires discontinuation:
    - AST or ALT > 5-10x ULN for > 2 weeks
    - AST or ALT > 10x ULN
    - Total bilirubin > 5x ULN
    - Concurrent AST or ALT > 3x ULN and total bilirubin > 2x ULN
- Any Grade 4 drug-related adverse event or laboratory abnormality, except for the following events:
  - Grade 4 neutropenia  $\leq$  7 days does not require discontinuation
  - Grade 4 lymphopenia or leukopenia does not require discontinuation
  - Isolated Grade 4 electrolyte imbalances/abnormalities that are not associated with clinical sequelae and are corrected with supplementation/appropriate management within 72 hours of their onset do not require discontinuation
  - Isolated Grade 4 amylase or lipase abnormalities not associated with symptoms or clinical manifestations of pancreatitis. The PI and Data Monitoring Committee (DMC) should be notified of Grade 4 amylase or lipase abnormalities (please do so by sending an email to [[contact]](mailto:[contact]))
- Any dosing interruption lasting > 6 weeks with the following exceptions:
  - Dosing interruptions to manage drug-related adverse events, such as prolonged steroid tapers, are allowed. Prior to re-initiating treatment in a subject with a dosing interruption lasting > 6 weeks, the PI and DMC should be consulted (by emailing [[contact]](mailto:[contact])). Tumor assessments should continue as per protocol even if dosing is interrupted.

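### Section 4.2 gives two differing delay rules for one case: a drug-related Grade 2 AST, ALT or total bilirubin in a patient whose baseline was normal

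*Combined protocol and SAP*

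**What the plan says.** Section 4.2 allows no dose modification for toxicity, so delay and discontinuation are the only dose actions. Its delay list runs as follows.

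- The general rule is to delay for a drug-related event of Grade 2 or above that is "non-skin, drug-related adverse event, with the following exceptions".
- The first exception reads "Grade 2 drug-related fatigue or laboratory abnormalities do not require a treatment delay". It names no test and refers to no other line.
- A later line reads "Any Grade 3 drug-related laboratory abnormality, with the following exceptions for lymphopenia, leukopenia, AST, ALT, or total bilirubin". Two liver lines stand beneath it.
- The first liver line begins "If a subject has a baseline AST, ALT or total bilirubin that is within normal limits, delay dosing for drug-related Grade"; the threshold that follows is Grade 2 or above.
- The second begins "If a subject has baseline AST, ALT, or total bilirubin within the Grade 1 toxicity range, delay dosing for drug-related Grade"; the threshold that follows is Grade 3 or above.
- A closing line leaves room for any event or laboratory finding that, in the investigator's view, "warrants delaying the dose of study medication".

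Section 4.2 also sends sites to management algorithms, including a hepatic one, in Appendix D and the Investigator Brochure.

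**The concern.** A patient enters with normal ALT and later has a drug-related Grade 2 ALT. One sentence says that no delay is needed; another says to delay. Neither mentions the other. The sentence that directs the delay is introduced as qualifying the Grade 3 laboratory line, although its own threshold is Grade 2, so on its placement it does not qualify the Grade 2 exemption.

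This is an operative dose-hold rule for liver toxicity. The schedule in Section 5.0 has a chemistry panel that includes AST, ALT and total bilirubin at every dosing visit, so the question can come up at any dose. Section 3.0 names a lead site and three participating sites, and a shared local reading cannot be taken for granted. Section 11.5 requires the study to be run as written. The same dosing decision could therefore be logged as compliant under one sentence and as a deviation under the other. Safety and tolerability is a secondary objective (2.2.3).

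**Working it through.** No power, error-rate or sample-size figure bears on this point. The check is a comparison of the two sentences, case by case.

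**Step 1. Apply both sentences to each case that the liver lines name** (drug-related AST, ALT or total bilirubin).

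| Baseline | On-study grade | Grade 2 exemption | Liver lines | Result |
|---|---|---|---|---|
| Normal | 2 | Delay not required | Delay | Differ |
| Grade 1 range | 2 | Delay not required | No trigger below Grade 3 | Agree |
| Normal | 3 | Does not apply | Delay | No conflict |
| Grade 1 range | 3 | Does not apply | Delay | No conflict |

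The sentences differ in one row only.

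**Step 2. See what each sentence does if it governs.**

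- If the exemption governs, the effective delay threshold is Grade 3 for a normal baseline and Grade 3 for a Grade 1 baseline. The split by baseline then does nothing.
- If the liver lines govern, the thresholds are Grade 2 and Grade 3, and every line has a function.

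This suggests that the liver lines were meant as a carve-out. It is an inference about drafting intent. The text does not state it.

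**Step 3. Look elsewhere for a statement of which governs.**

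- Section 4.1 says only that delays follow specific laboratory and event criteria. Those criteria are the lines in question.
- Section 4.2.1 deals with permanent discontinuation and does not say when a Grade 2 value calls for a delay.
- The footnotes of the hepatic algorithm in Appendix D cover when therapy may be delayed instead of discontinued, and a starting steroid dose for Grade 4. They do not address Grade 2. The flowchart itself was not in the text available to me, nor was the Investigator Brochure.

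**Step 4. Try to size it.** The number affected is the number treated × the share with a normal baseline × the share of those who then have a drug-related Grade 2 value. The documents give neither share. Section 8.1.13 lists increased AST in 28% and increased ALT in 16%, and 33 × 0.28 = 9.2 and 33 × 0.16 = 5.3. These do not measure the overlap. The rates have no grade split, come from melanoma and squamous lung cancer patients, and are not restricted to normal baselines. Section 3.1.6 admits AST and ALT up to 3 × ULN, or 5 × ULN with liver metastases. No rate is listed for bilirubin.

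**The case against.** The strongest reply is that a specific rule displaces a general one. The liver lines name their three tests, condition on baseline and are labelled as exceptions; the Grade 2 exemption is generic. Step 2 supports this, and I accept it as the more natural reading. It narrows the point but does not remove it. The exemption gives a complete answer to anyone who stops there, and the carve-out is attached to a different line.

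A reader might infer that the protocol gives flatly opposite orders and directs sites to dose through a Grade 2 liver abnormality. The documents do not support that. The exemption says that a delay is not required, which permits dosing without ordering it. A site that delays satisfies both sentences, and the investigator may delay in any case. What remains open is whether the protocol requires the delay.

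A reader might also infer that Grade 3 skin and Grade 3 laboratory events are exempt from delay, because "Any Grade 3 skin, drug-related adverse event" and the Grade 3 laboratory line are printed beneath the exceptions to a non-skin rule, while the general Grade 3 stop in Section 4.2.1 covers "Any Grade 3 non-skin, drug-related adverse event lasting > 7 days". That reading rests on indentation, which may have been lost when the PDF was converted. The wording points the other way. A skin event cannot be an exception to a non-skin rule, and exempting Grade 3 lymphopenia or leukopenia would be pointless if all Grade 3 laboratory events were already exempt. It is something to check in the source file and is not a finding.

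Finally, the full hepatic algorithm may give sites a clear answer. That is possible, and it is why I do not claim that sites would in fact act differently.

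**Conclusion.** The point holds as a limited drafting conflict. For a drug-related Grade 2 AST, ALT or total bilirubin in a patient with a normal baseline, Section 4.2 contains two sentences that differ, and no text available to me says which prevails. The liver line is probably the intended rule for these tests, but the list does not say so. In the other cases compared, the lines agree or do not meet.

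The number of patients affected is unknown. Different dosing or different toxicity data between sites is a possibility, not something the documents show. The primary response analysis, the two-stage decision rule and the sample size are unaffected. The conclusion assumes that the liver lines belong under the Grade 3 laboratory line, as their introductory wording indicates, and that the hepatic flowchart does not settle the matter. The point still merits correction because it sits in a dose-hold rule that bears on patient safety, and the correction is cheap.

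**What to change.** Reconcile the two sentences in Section 4.2. State once which of them governs AST, ALT and total bilirubin, and put a cross-reference to it in the other. Check that the result matches the hepatic algorithm in Appendix D. Which rule applies is a clinical decision for the sponsor, and no view is taken on it here.

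In the same amendment, check in the source document that the Grade 3 skin and Grade 3 laboratory lines are printed at the list level that shows whether they trigger a delay or are exceptions to one.

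The cost is the wording of one list. No visits, tests, data fields or analyses change.

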##### **4.2.1 Treatment discontinuation criteria**

Nivolumab treatment should be permanently discontinued for the following:

- Any Grade 2 drug-related uveitis, eye pain or blurred vision that does not respond to topical therapy and does not improve to Grade 1 severity
- Any Grade 3 non-skin, drug-related adverse event lasting > 7 days
- Grade 3 drug-related uveitis, pneumonitis, bronchospasm, hypersensitivity reaction, or infusion reaction of any duration requires discontinuation
- Grade 3 drug-related laboratory abnormalities do not require treatment discontinuation except:
  - Grade 3 drug-related thrombocytopenia > 7 days or associated with bleeding requires discontinuation
  - Any drug-related liver function test (LFT) abnormality that meets the following criteria requires discontinuation:
    - AST or ALT > 5-10x ULN for > 2 weeks
    - AST or ALT > 10x ULN
    - Total bilirubin > 5x ULN
    - Concurrent AST or ALT > 3x ULN and total bilirubin > 2x ULN
- Any Grade 4 drug-related adverse event or laboratory abnormality, except for the following events:
  - Grade 4 neutropenia  $\leq$  7 days does not require discontinuation
  - Grade 4 lymphopenia or leukopenia does not require discontinuation
  - Isolated Grade 4 electrolyte imbalances/abnormalities that are not associated with clinical sequelae and are corrected with supplementation/appropriate management within 72 hours of their onset do not require discontinuation
  - Isolated Grade 4 amylase or lipase abnormalities not associated with symptoms or clinical manifestations of pancreatitis. The PI and Data Monitoring Committee (DMC) should be notified of Grade 4 amylase or lipase abnormalities (please do so by sending an email to [[contact]](mailto:[contact]))
- Any dosing interruption lasting > 6 weeks with the following exceptions:
  - Dosing interruptions to manage drug-related adverse events, such as prolonged steroid tapers, are allowed. Prior to re-initiating treatment in a subject with a dosing interruption lasting > 6 weeks, the PI and DMC should be consulted (by emailing [[contact]](mailto:[contact])). Tumor assessments should continue as per protocol even if dosing is interrupted.
  - Dosing interruptions > 6 weeks that occur for non-drug-related reasons may be allowed if approved by the PI and DMC. Prior to re-initiating treatment in a subject with a dosing interruption lasting > 6 weeks, the PI and DMC designee must be consulted. Tumor assessments should continue as per protocol even if dosing is interrupted.

- Any adverse event, laboratory abnormality, or intercurrent illness which, in the judgment of the Investigator, presents a substantial clinical risk to the subject with continued nivolumab dosing.

**4.2.2 Treatment of nivolumab-related infusion reactions**

Since nivolumab contains only human immunoglobulin protein sequences, it is unlikely to be immunogenic and induce infusion or hypersensitivity reactions. However, if such a reaction were to occur, it might manifest with fever, chills, rigors, headache, rash, pruritus, arthralgias, hypotension, hypertension, bronchospasm, or other allergic-like reactions. All grade 3 or 4 infusion reactions should be reported within 24 hours to the study QAM and reported as an SAE if it meets the criteria. Infusion reactions should be graded according to NCI CTCAE (Version 4.0.3) guidelines.

Treatment recommendations are provided below and may be modified based on local treatment standards and guidelines, as appropriate:

NCI CTCAE Grade	Treatment	Premedication at subsequent dosing

Grade 1 Mild reaction; infusion interruption not indicated; intervention not indicated
	
Remain at bedside and monitor subject until recovery from symptoms.
	
The following prophylactic pre-medications are recommended for future infusions:
 
 
• Diphenhydramine 50 mg (or equivalent) and/or
 
• Acetaminophen/paracetamol 325 to 1000 mg at least 30 minutes before additional nivolumab administrations
 


Grade 2 Moderate reaction requires therapy or infusion interruption but responds promptly to symptomatic treatment [eg, antihistamines, non-steroidal anti-inflammatory drugs, narcotics, corticosteroids, bronchodilators, IV fluids]; prophylactic medications indicated for < 24 hours
	
Stop the nivolumab infusion, begin an IV infusion of normal saline, and treat the subject with diphenhydramine 50 mg IV (or equivalent) and/or acetaminophen/paracetamol 325 to 1000 mg;
 
Remain at bedside and monitor subject until resolution of symptoms.
 
Corticosteroid and/or bronchodilator therapy may also be administered as appropriate. If the infusion is interrupted, then restart the infusion at 50% of the original infusion rate when symptoms resolve; if no further complications ensue after 30 minutes, the rate may be increased to 100% of the original infusion rate.
	
For future infusions, the following prophylactic pre-medications are recommended:
 
 
• Diphenhydramine 50 mg (or equivalent) and/or
 
• Acetaminophen/paracetamol 325 to 1000 mg should be administered at least 30 minutes before nivolumab infusions. If necessary, corticosteroids (up to 25 mg of SoluCortef or equivalent) may be used.
 

	
Monitor subject closely. If symptoms recur, then no further nivolumab will be administered at that visit.
	

Grades 3 or 4 Severe reaction, Grade 3: prolonged [ie, not rapidly responsive to symptomatic medication and/or brief interruption of infusion]; recurrence of symptoms following initial improvement; hospitalization indicated for other clinical sequelae [eg, renal impairment, pulmonary infiltrates]. Grade 4: Life-threatening; pressor or ventilatory support indicated
	
Immediately discontinue infusion of nivolumab. Begin an IV infusion of normal saline and treat the subject as follows: Recommend bronchodilators, epinephrine 0.2 to 1 mg of a 1:1000 solution for subcutaneous administration or 0.1 to 0.25 mg of a 1:10,000 solution injected slowly for IV administration, and/or diphenhydramine 50 mg IV with methylprednisolone 100 mg IV (or equivalent), as needed.
 
Subject should be monitored until the Investigator is comfortable that the symptoms will not recur. Nivolumab will be permanently discontinued. Investigators should follow their institutional guidelines for the treatment of anaphylaxis. Remain at bedside and monitor subject until recovery of the symptoms
 
In case of late-occurring hypersensitivity symptoms (eg, appearance of a localized or generalized pruritus within 1 week after treatment), symptomatic treatment may be given (eg, oral antihistamine or corticosteroids)
	
No subsequent dosing

**4.2.3 Treatment with nivolumab beyond progression**

A minority of subjects treated with immunotherapy may derive clinical benefit (either delayed responses, stable disease, or increased overall survival) despite initial evidence of progressive disease (PD) with nivolumab.

Patients may be permitted to continue treatment beyond initial RECIST 1.1-defined PD occurring during the initial treatment period (up to 12 weeks) as long as they meet the following criteria:

- No more than 4 new lesions, total sum of the longest diameter (SHORT diameter for LN) cannot exceed 40% of the initial sum including new lesions
- Patients must be clinically stable with no change in performance status due to disease progression

- No indication for immediate alternative treatment
- Patient [assessed by the investigator] is showing clinical benefit and tolerates study drug. The assessment of clinical benefit should take into account whether the subject is clinically stable or deteriorating and likely or unlikely to receive further benefit from continued treatment.
- The time of progression is noted from the first assessment that exceeds standard criteria

New lesions are considered measurable at the time of initial progression if the longest diameter is at least 10 mm (except for pathological lymph nodes, which must have a short axis of at least 15 mm). Any new lesion considered non-measurable at the time of initial progression may become measurable and therefore included in the tumor burden measurement if the longest diameter increases to at least 10 mm (except for pathological lymph nodes, which must have an increase in short axis to at least 15 mm).

Patients are allowed to continue treatment after initial disease progression for 2-3 additional doses (4-6 weeks) only after consulting with the study PI. These patients must be reassessed for response within 8 weeks; the scan initially confirming PD should be used as a new baseline. If two consecutive scans confirm PD, the patient should come off treatment. However, as long as subsequent scans show a response equal to or better than Stable Disease (SD), the patient may continue receiving treatment every 2 weeks, and must have scans every 8 weeks. Treatment may continue up to an additional 30% total single diameter increased over baseline. New measureable lesions are not permitted with this schema

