## **4.0 TREATMENT PLAN**

This will be a single-center phase II trial with patients with metastatic or locally advanced ACC who have been treated with at least one line of therapy including mitotane and/or chemotherapy. Patients will be treated with nivolumab 240mg as an intravenous infusion over 30 minutes every 2 weeks until confirmed disease progression, unacceptable toxicity, or withdrawal of consent. Note: Please refer to section 4.2.3 for patients who may continue treatment after initial progression.

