#### **4.4 Duration of Therapy**

In the absence of treatment delays due to adverse event(s), treatment may continue until one of the following criteria applies:

- Disease progression (please refer to 4.2.3 for guidance regarding treatment beyond progression),
- Intercurrent illness that prevents further administration of treatment,
- Unacceptable adverse event(s) as already described in session.

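### Section 4.2.3 caps the tumour sum for treatment beyond progression at 40% of the initial sum, when target-lesion progression at week 8 needs at least 120%; an increase of at most 40% is probably meant

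*Combined protocol and SAP*

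**What the plan says.** Section 4.2.3 applies to patients whose initial RECIST 1.1 progression falls within the first 12 weeks. Its first bullet tolerates up to four new lesions and adds that the "total sum of the longest diameter (SHORT diameter for LN) cannot exceed 40% of the initial sum including new lesions". The bullet does not use the word increase. Further bullets require clinical stability, no need for immediate alternative treatment, and investigator-judged benefit with tolerance of the drug. Continuation is then allowed "for 2-3 additional doses (4-6 weeks) only after consulting with the study PI".

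After that, "the scan initially confirming PD should be used as a new baseline". Three sentences govern what follows:

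- "If two consecutive scans confirm PD, the patient should come off treatment".
- "as long as subsequent scans show a response equal to or better than Stable Disease (SD), the patient may continue receiving treatment".
- "Treatment may continue up to an additional 30% total single diameter increased over baseline".

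The section closes by ruling out new measurable lesions, without saying at which stage.

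Other sections rely on this text. Section 4.0 says "Please refer to section 4.2.3 for patients who may continue treatment after initial progression" and section 4.4 says "please refer to 4.2.3 for guidance regarding treatment beyond progression". Footnote 3 of section 5.0 sends the reader to the same place.

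**The concern.** The section exists to keep on treatment some patients whose tumours have grown or who have new lesions. A ceiling of 40% of the initial sum asks instead for a tumour burden less than half of what it was at the start. Followed to the letter, as section 11.5 requires outside emergencies, the criterion shuts out the patients whom the section is written for. The alternative is that each site silently substitutes its own reading of a numerical limit. Section 3.0 names four institutions. What is at stake is an individual decision to continue or stop nivolumab.

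**Working it through.** **Inputs**

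- Entry cap: 40% of the initial sum S, new lesions included (section 4.2.3).
- Window: progression within 12 weeks (section 4.2.3).
- Scans: week 8, then week 16, each with a window of at most one week (section 5.0 footnote 3; section 6.1). Only the week-8 scan is scheduled inside 12 weeks.
- Target-lesion progression: growth of at least 20% and at least 5 mm over the smallest sum on study, baseline included (section 6.2.3.1). At week 8 the only earlier scheduled sum is S.

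**Entry cap, taking S = 100 mm as an illustration**

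1. Literal cap: 0.40 × 100 = 40 mm.
2. Smallest sum that is target-lesion progression at week 8: max(1.2 × 100, 100 + 5) = 120 mm. Ratio 120/40 = 3. The ratio is 3 for any S of 25 mm or more. Below that the 5 mm rule raises it: for S = 20 mm the cap is 8 mm, progression starts at 25 mm, and 25/8 = 3.1.
3. Progression by new or non-target lesions alone: the total must be at most 0.40 × S, a fall of at least 60%. With one new 10 mm lesion and S = 100 mm, the target lesions may sum to at most 40 − 10 = 30 mm, a 70% fall.
4. Unscheduled scan with earlier shrinkage to N: target-lesion progression meets the cap only if max(1.2N, N + 5) ≤ 0.40S, so N ≤ min(S/3, 0.40S − 5). For S = 100 mm, N ≤ 33.3 mm. For S = 50 mm, N ≤ 15 mm. The 5 mm rule is the binding one for S below 75 mm.
5. Cap read as an increase: 1.40 × 100 = 140 mm, so target-lesion progression from 120 to 140 mm meets the size criterion.

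| Week-8 finding, S = 100 mm | Total | Literal cap (40 mm) | Increase of at most 40% (140 mm) |
|---|---|---|---|
| Targets grow, no new lesion | 125 mm | fails | meets (+25%) |
| Targets grow, no new lesion | 145 mm | fails | fails (+45%) |
| Targets unchanged, one new 12 mm lesion | 112 mm | fails | meets (+12%), but see below |

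The last row has a second obstacle. Section 4.2.3 counts a new non-nodal lesion of 10 mm or more as measurable, and its closing sentence bars new measurable lesions. If that sentence applies at entry, this patient is out on either reading of the cap. If it applies only after re-baselining, the first bullet's allowance of four new lesions governs and the patient may continue.

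**The 30% sentence, taking S = 100 mm and a progression scan of 125 mm**

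If the progression scan is the new reference and the sum does not shrink afterwards, stable disease ends below max(1.2 × 125, 125 + 5) = 150 mm.

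| Meaning of the additional 30% | Limit | Against 150 mm |
|---|---|---|
| 30% over the progression scan | 1.3 × 125 = 162.5 mm | looser; 150 to 162.5 mm is progression yet permitted |
| 30% of the original sum, added to the progression scan | 125 + 30 = 155 mm | looser; 150 to 155 mm |
| 130% of the original sum | 130 mm | tighter; sums above 130 and below 150 mm are stable yet over the limit |

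On the first reading the overlap exists only for new baselines above 5/0.30 = 16.7 mm.

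**The case against.** The strongest reply on the cap is that nobody would apply it literally. A section that admits progressing patients cannot sensibly demand a 60% shrinkage, and every entry needs consultation with the study PI, so wide divergence between sites is unlikely. Both points are fair and limit the practical harm. They do not make the number right: the documents nowhere state the intended limit, and it decides whether a patient stays on treatment. One could also read the 40% as limiting only the new lesions' contribution, but the sentence speaks of a total sum that includes them.

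Three stronger readings may tempt a reader, and the documents do not support them.

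- *No progressing patient could ever qualify.* This holds for target-lesion progression at the scheduled week-8 scan. New-lesion or non-target progression with deep shrinkage, or an unscheduled scan after a low nadir, is not strictly excluded.
- *The 30% sentence contradicts the stable-disease sentence.* A coherent reading exists: continue while stable or better; after one progression scan within 30%, wait for the next; stop after two in a row or beyond 30%. The stable-disease sentence is permissive, and the explicit stopping rule is the two-scan one. The size of any conflict, and even its direction, depends on which baseline is meant. The progression scan is the most natural reading, given the re-baselining sentence and the word additional, but the text does not settle it.
- *The trial's results are compromised.* Section 4.2.3 dates progression from the first assessment that exceeds standard criteria, and section 6.2.3.3 takes best response up to progression. The definitions of ORR, PFS and OS and the two-stage boundaries do not depend on these limits.

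**Conclusion.** The entry cap is wrong as written. At the only scheduled scan in the window it is one third of the smallest sum that counts as target-lesion progression, and less than a third for initial sums below 25 mm. That conclusion rests only on the section's wording, the scan schedule and the RECIST definitions in section 6.2.3.1. That an increase of at most 40% was meant is an inference from the section's purpose, which the investigators should confirm.

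The 30% sentence needs clarification and nothing stronger. It leaves growth of 20% to 30% over the progression scan both progressive and permitted on one reading, and it is the tighter limit on another.

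Only patients who progress in the first 12 weeks are affected, out of up to 33 enrolled. The documents do not give their number, and the clinical-stability, benefit and toxicity conditions still apply to them.

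**What to change.** 1. Reword the cap: *the total sum, including measurable new lesions, must not increase by more than 40% over the initial sum*. For 100 mm this gives 140 mm in place of 40 mm.
2. State that the closing bar on new measurable lesions applies after re-baselining, if that is the intent, so that it does not cancel the first bullet's allowance of up to four new lesions.
3. Have the investigators state which baseline the additional 30% refers to, and whether it is an interim ceiling for a single progression scan until two consecutive ones end treatment.

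Deleting the 30% sentence, or replacing it with the 20% RECIST threshold at every later scan, is not proposed here. Either is a clinical choice: some patients could stop earlier, and a single progression scan after re-baselining could end treatment, which would undercut the two-scan rule.

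The cost is a wording amendment with clinical sign-off. Sample size and analysis do not change.
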